## **1.0 STATISTICAL ANALYSES**

### **1.1 Primary Outcome**

The single primary objective of this trial is to discover whether there is a difference in the proportion achieving HIV viral suppression amongst the three study groups: (1) Patient Navigator, (2) Patient Navigator plus Contingency Management and (3) Treatment as Usual. There are three primary hypotheses,  $arm1 = arm2$ ,  $arm1 = arm3$ , and  $arm2 = arm3$ . The family-wise error rate for these hypotheses is controlled to be no greater than .05.

The primary outcome variable is binary: presence of HIV viral suppression ( $\leq 200$  copies/ml) at the 12 month follow-up versus presence of viral load  $> 200$  or death (all-cause mortality). Viral suppression is defined as a viral load  $\leq 200$  copies/ml rather than achieving a viral load “below the limit of detection of the assay” which, in this day, is usually  $< 50$  copies/ml to avoid “blips” and episodes of low level viremia that are not uncommon, even among patients on stable antiretroviral therapy.

### **1.2 Protocol Violations**

Protocol Violations will be summarized for each arm of the study. The number of participants with violations as well as frequencies and percents for the types of protocol violations will be presented.

### **1.3 Treatment Exposure**

Treatment exposure will be summarized by arm and site, comparing the expected with observed number of Patient Navigator sessions attended (only among the two arms where participants randomized to Patient Navigator sessions).

### **1.4 Analysis of Participant Characteristics**

Baseline demographic and clinical variables will be summarized for each arm of the study. Descriptive summaries of the distribution of continuous baseline variables will be presented with mean, median, minimum, maximum and standard deviation. Categorical variables will be summarized in terms of frequencies and percentages. Since randomization is expected to produce balance at baseline among the three arms of the trial, statistical comparisons of treatment arms with respect to baseline characteristics should be more informal. If differences among treatment arms are suspected, statistical testing will be performed.

### **1.5 Participant Disposition**

The visit completion status and the reason for early discontinuation of the study will be summarized by site and treatment arm with descriptive statistics. These include counts and percentages for each reason for discontinuation.

The number of randomizations and reasons for ineligibility will also be summarized.

### **1.6 Statistical Methods for Primary Analysis**

The primary hypothesis test will compare the proportions achieving HIV viral suppression at 12 months across the three study groups. Death from any cause will be considered equivalent to non-suppression for the purposes of calculating this proportion. (Differences in outcome when deaths are categorized with respect to likelihood of being HIV and/or drug use related will be explored in a secondary analysis.) All treatment comparisons will be performed under the Intent-to-Treat (ITT) criterion in the sense that participants will be analyzed in the arm to which they were randomized, regardless of subsequent events. However, participants who are lost to follow-up before 6 months will not contribute to the primary analysis. A Generalized Estimating

Equations (GEE) model will be employed (Zeger & Liang, 1986) with a binomial distribution and logit link as implemented in SAS. The GEE model will include both 6-month and 12-month HIV viral suppression status. However, the primary test of the hypothesis will be based on contrasts involving the 12-month proportions only. This model gains statistical power by pooling the error term across the two follow-up times and is closer to an ITT approach than would be the analysis of 12-month events only. It does not impute data that are missing at month 12 with the exception of death, which will be considered equivalent to non-suppression. Any potential correlation between patients within a site will be controlled by estimating a fixed effect for site in this model.

A simple closed-testing procedure (Westfall, Tobias, Rom, Wolfinger, & Hochberg, 1999) will be used to control family-wide type I error at 0.05 while still allowing all three pairwise comparisons between arms. Specifically, let  $P(123)$  be the (two-sided) p-value of the contrast testing equality among all three arms, while  $P(12)$ ,  $P(13)$ , and  $P(23)$  are the (two-sided) p-values for arms 1&2, 1&3, and 2&3, respectively. Then, let the adjusted p-value for the (1,2) comparison be

$$P^*(12) = \max[P(123), P(12)]$$

and similarly for the other pairwise comparisons. Tests of pairwise equality will be performed by comparing  $P^*(12)$ ,  $P^*(13)$ , and  $P^*(23)$  to the 0.05 level of significance.

### 1.6.1 Covariates including Site

Randomization should ensure that the distributions of characteristics across our 3 groups are similar at baseline. Thus, the analysis is straightforward, and the primary analysis of association of the particular contrasts of group on the particular outcome will not need to control for covariates, with the exception of an indicator of baseline CD4 count (greater than 350 cells/uL), an indicator of detectable viral load at baseline, and site of recruitment. Site will be included as a covariate because there is the possibility that participants within a site will be more alike than will be participants from different sites. If ignored, this would violate an assumption of the simple model that all observed participants are independent of each other. Inclusion of site as a covariate will correct the model for any dependence in observations within a site, and baseline viral load and CD4 count may prove important predictors. As noted, randomization should control for all other participant level covariates. Nevertheless, to assess the effects of and control for any unintended impact of group differentials across the range of covariates, in a second sensitivity analysis, the simple analysis listed above will be extended to additionally control for age at baseline, race and ethnicity, gender, and primary type of drug use (injection drug use vs. non-injection drug use, and opiate vs. non-opiate, stimulant vs. non-stimulant). The significance levels for any of these covariates will be reported, but will not affect the conclusions of the primary analysis. As listed below, the effects of these variables on viral suppression will be explored more fully in the secondary aims. We will also assess the interaction of each of these covariates with treatment group as they affect the primary outcomes. If statistically significant, the results of these analyses will not affect the p-value of the primary analyses, but may affect our interpretation. However, the results will be reported in the secondary analyses sections.

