### 1.6.2 SAS Code for Primary Analysis

SAS code suitable for performing the primary analysis follows. In this code, it is assumed that non-suppression and death from any cause have been lumped together as outcomes. The p-values from the four contrasts will be used in the closed testing.

```
proc genmod data = all;  
  class arm time patid site vloadbase cd4base;  
  model outcome = vloadbase cd4base site arm time time * arm / dist = bin;
```

```
repeated subject = patid / type = exch;  
contrast "TAU NAV" arm 1 -1 0 time * arm 0 1 0 -1 0 0;  
contrast "TAU NAVCM" arm 1 0 -1 time * arm 0 1 0 0 0 -1;  
contrast "NAV NAVCM" arm 0 1 -1 time * arm 0 0 0 1 0 -1;  
contrast "TAU NAV NAVCM" arm 1 -1 0 time * arm 0 1 0 -1 0 0,  
      arm 1 0 -1 time * arm 0 1 0 0 0 -1;  
run;
```

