## 1.7 Rationale for Sample Size and Statistical Power

Power calculations were based on a simulation of several scenarios, with 5000 iterations per scenario. In each iteration, 266 virally unsuppressed participants were recruited to each of three treatment groups, after which death and dropout rates, and rates of suppression before and after 6 months, were imposed so as to result in proportions of simulated participants dead, lost, suppressed, and unsuppressed at both 6 and 12 months as indicated below. These rates characterized the scenario. (Note that the rates dictate the probabilities of joint occurrences of outcomes at 6 and 12 months, but it is possible for more than one set of rates to produce the same set of 6-month and 12-month margins.)

Once these data were simulated, they were subjected to a Generalized Estimating Equation (GEE) analysis in which dropouts were ignored and dead participants were combined with unsuppressed participants. More specifically, the GEE regressed state (suppressed versus unsuppressed or dead) on time (6 months, 12 months), treatment group (Patient Navigator = PN, Contingency Management + Patient Navigator = CM, Treatment as usual = TAU) site (1-10) and the time by treatment group interaction using a binomial link. The outcome of interest was the proportion suppressed (versus unsuppressed or dead) in each arm at 12 months, but the analysis incorporated 6-month data so that the 6-month/12-month correlation could in part offset loss to follow-up between 6 and 12 months. Contrasts were used to obtain p-values for the hypotheses CM=PN=TAU, CM=PN, CM=TAU, and PN=TAU with respect to the outcome of interest.

These p-values were combined together using the closed-testing methodology explained in Section 1.6. Note was taken of which of the pairwise hypotheses were rejected ( $\alpha = 0.05$ , two-tailed), and which accepted according to the Closed testing algorithm in each iteration. Finally, the power for the tests of the various hypotheses was estimated as the proportion of the 5000 iterations in which each hypothesis was rejected.

The scenarios were defined by the following parametric values, which varied from treatment group to treatment group:

- M6 = target suppressed proportion at 6 months (assuming no death or dropout)
- M12 = target suppressed proportion at 12 months (assuming no death or dropout)
- S = Probability that a participant will be suppressed at 12 months, given he was suppressed at 6 months

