#### 1.9.1 HIV Related Secondary Outcomes

The data associated with the HIV secondary outcomes include binary (Yes/No), count and continuously distributed data. In the following list of HIV secondary outcomes the expected distribution is in parenthesis:

- a) Repeat primary analysis with the addition of a treatment interaction with viral suppression status at baseline (binary)

- b) Viral suppression at 12 months or HIV-related deaths (binary, note that non-HIV related deaths would be classified as missing in this analysis)
- c) Viral suppression at 6 months (binary)
- d) CD4 Cell count (continuous at 6 and 12 months)
- e) Engagement into care (visit constancy, a repeated binary at 3-month intervals)
- f) HIV care visit attendance (count)
- g) Medication Adherence (count)
- h) Hospitalizations (count)
- i) All cause mortality (binary)

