#### 1.10.1 Tests of the Secondary Outcomes

Each of the stated secondary outcomes listed in Section 1.9 will be tested separately, using the closed testing procedures described for the primary outcome to control family-wide type I error. The statistical methods used will also mirror the methods used for the primary hypothesis. Those secondary outcomes that are binary will be tested as described for the primary hypothesis using a logistic regression; whereas those secondary outcomes that involve either continuous or ordinal variables will utilize the appropriate distribution and link function. Note that the exact method of analysis will depend on the realized distribution of the particular outcome in this trial for example, an expected count data variable may need to be modeled using a zero-inflated Poisson Regression rather than a Poisson regression if there are too many zero observations to fit the standard Poisson. If there is over-dispersion, a negative binomial (or zero-inflated negative binomial) regression may be appropriate. The hypothesized

moderator variables (for viral suppression: psychological distress, housing instability, food insecurity, health literacy, HIV-related cognitive function, renal function and liver function; and CD4 count. Drug Use moderator: readiness for treatment and HCV status) will be addressed in the same way that the covariates for the planned sensitivity analysis of the primary outcomes (site, age at baseline, race and ethnicity, gender, and primary type of drug use [IV vs. non-IV, opiate vs. non-opiate, and stimulant vs. non-stimulant], baseline level of viral load) will be addressed. Models will be estimated with main effects for these variables, a main effect for randomization group and an interaction between the particular variable and randomized group on the primary outcomes. For these analyses, the overall Type I error will not be controlled, rather, the reader of any resulting journal article will be alerted to the fact that these analyses were the result of *post-hoc* exploratory analyses, and that any statistically significant results may have resulted from a Type I error, and require replication.

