### **1.11 Factors for Stratification**

Randomization will be stratified only by site. Site, baseline viral load, and baseline CD4 count will be used as covariates in the primary analysis.

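### The continuous follow-up CD4 outcome would be adjusted for its own baseline only as above or below 350, which gives up avoidable precision for that secondary outcome

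*SAP*

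**What the plan says.** - **Form of the covariate.** SAP 1.6.1 includes "an indicator of baseline CD4 count (greater than 350 cells/uL" in the primary model, with an indicator of detectable baseline viral load and site. The reason given is prognostic: "baseline viral load and CD4 count may prove important predictors". No reason is given for cutting at 350.
- **Code.** SAP 1.6.2 agrees with the text; the class statement reads "class arm time patid site vloadbase cd4base", so cd4base is categorical.
- **Short form.** SAP 1.11 says "Site, baseline viral load, and baseline CD4 count will be used as covariates in the primary analysis", without coding for either laboratory value.
- **CD4 as an outcome.** SAP 1.9.1 d lists "CD4 Cell count (continuous at 6 and 12 months".
- **Secondary methods.** SAP 1.10.1 says "The statistical methods used will also mirror the methods used for the primary hypothesis". What it then varies by outcome is the distribution and the link function. It gives no separate covariate list for CD4.

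**The concern.** When a continuous measurement is analysed at follow-up, its own baseline is usually the best available predictor, and adjusting for it is the main source of extra precision. Read together, 1.6.1, 1.6.2 and 1.10.1 supply that adjustment only as a two-level term. Patients who start at 20 and at 340 cells/uL are treated as having the same baseline. The count must be known to form the indicator, so the rest of the information is discarded at no saving in data collection.

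At stake is the width of the intervals for the between-arm differences in CD4 at 6 and 12 months. Validity is not at stake: the adjustment is pre-specified and the arms are randomized.

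**Working it through.** **1. The plan's own figure.** The SAP states no precision gain from baseline CD4. The nearest stated figure is the power in 1.7, where "In each iteration, 266 virally unsuppressed participants were recruited to each of three treatment groups". The model used there has time, arm, site and time by arm, and no CD4 term. A simulation from the scenario parameters in 1.7 used 266 per arm, deaths as failures, dropouts as missing, an exchangeable logit GEE with 12-month contrasts, closed testing at 0.05 and 3,000 runs. Site was left out because no site effect is stated, and the unsuppressed death rate was applied to everyone in the first two quarters. Power in percent:

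| Scenario | TAU vs PN, stated / reproduced | PN vs CM, stated / reproduced | TAU vs CM, stated / reproduced |
|---|---|---|---|
| A | 93 / 91.2 | 87 / 86.0 | 100 / 100 |
| B | 94 / 94.2 | 92 / 90.5 | 100 / 100 |
| C | 93 / 91.3 | 89 / 88.5 | 100 / 100 |
| D | 94 / 93.7 | 89 / 89.5 | 100 / 100 |

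All 12 cells agree within 2 points. The stated power stands and does not depend on how CD4 is coded.

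**2. Information kept by the cut.** Let q be the share of patients above 350 and c the matching normal cut-point. On a normal scale, the squared correlation between the count and its indicator is k = φ(c)² / [q(1 − q)].

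- q = 0.5: 0.3989² / 0.25 = 0.637
- q = 0.3: 0.3477² / 0.21 = 0.576
- q = 0.1: 0.1755² / 0.09 = 0.342

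On this scale, more than half of the baseline information is lost only when q is below about 0.21.

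**3. Effect on the follow-up CD4 outcome.** With baseline to follow-up correlation r, and one follow-up time taken by itself, the residual variance is 1 − r² with the continuous count and 1 − k·r² with the indicator. Relative efficiency is the first divided by the second.

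| r | q | Continuous | Indicator | Variance ratio | Efficiency lost |
|---|---|---|---|---|---|
| 0.5 | 0.5 | 0.750 | 0.841 | 1.12 | 11% |
| 0.5 | 0.1 | 0.750 | 0.914 | 1.22 | 18% |
| 0.6 | 0.5 | 0.640 | 0.771 | 1.20 | 17% |
| 0.6 | 0.1 | 0.640 | 0.877 | 1.37 | 27% |
| 0.8 | 0.5 | 0.360 | 0.593 | 1.65 | 39% |
| 0.8 | 0.1 | 0.360 | 0.781 | 2.17 | 54% |

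Standard errors are the square roots of the variance ratios: √1.12 ≈ 1.06 and √2.17 ≈ 1.47, so about 6% to 47% larger. The efficiency lost can be read as the share of the sample given up for this outcome.

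**4. Sensitivity to shape.** With skewed CD4 distributions analysed on the raw scale, the share of information kept ranges from about 27% to 65%. The size of the loss therefore also depends on the distribution and the scale of analysis.

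**5. Effect on the primary outcome.** Logistic simulation with 229 per arm (266 × 0.86, scenario A attrition of 14%), suppression of 16/29/42%, odds ratios of 1.25 to 2.0 per SD of CD4, and q from 0.1 to 0.5. Between indicator and continuous coding, TAU vs PN power differs by at most 1 point and PN vs CM by 0 to 3 points. The largest gap is 84.3% against 87.3%, at an odds ratio of 2.0 and q = 0.1. A second set, with log-odds of 0.4 to 0.8 per SD and q of 0.1 to 0.3, gave PN vs CM pairs of 83.4/83.9, 82.9/85.9, 83.6/83.7 and 86.5/87.7 (1,500 trials each, Monte Carlo standard error about 1 point).

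**The case against.** **The SAP never says that the CD4 model carries only the indicator.** Sections 1.6.1 and 1.11 set the covariates for the primary analysis, and 1.10.1 lets the exact method depend on the realized distribution. This stands in part: the reading is an inference. But the flexibility in 1.10.1 concerns distribution and link, and no other baseline adjustment appears anywhere. If another one is intended, it is unspecified.

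**The assumed r and q drive the size.** This stands. Neither is in the SAP, so only a range can be given, and its lower end is modest.

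**A two-level term assumes no shape for the relation, while a continuous term does.** This is a fair cost. The primary-outcome simulations also assume a linear log-odds relation, which favours the continuous form.

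**The confirmatory analysis is sound.** This stands. The closed procedure used to "control family-wide type I error at 0.05 while still allowing all three pairwise comparisons between arms" is unaffected, and CD4 is one of thirteen listed secondary outcomes (nine in 1.9.1, four in 1.9.2), which 1.12 promises to interpret conservatively.

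A reader might also infer that 1.11 contradicts 1.6.1 by naming the count. The documents do not support that. Section 1.11 shortens viral load in the same way, 1.6.1 itself uses the short form after defining both indicators, and the code agrees with the indicator. It is shorthand.

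**Conclusion.** The point holds for the continuous follow-up CD4 outcome. As the SAP is written, adjustment for baseline CD4 runs only through the 350 cut, at a cost of roughly 11-54% of the efficiency available from the continuous count. That range rests on normality, 10-50% of patients above 350 and a correlation of 0.5-0.8, all of them assumptions, and on reading the mirroring rule in 1.10.1 as carrying the indicator over unchanged.

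A reader might go further and infer that most of the available precision is lost across the models. That is not supported. For the primary test the difference is 0-3 power points. For the CD4 outcome, under normality, the cut keeps more than half of the baseline information unless fewer than about 21% of patients are above 350; skewed raw counts can move this either way, and the SAP gives neither the share nor the distribution. Type I error and the stated power of at least 87% are unaffected. This is an efficiency point about one secondary outcome, worth making because the remedy is so cheap.

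**What to change.** Add one sentence to 1.10.1: the models for CD4 count at 6 and 12 months adjust for baseline CD4 as a continuous covariate on a named scale, for example the square root of the count, in place of the indicator used for the primary outcome. In the program for that outcome, baseline CD4 then leaves the class statement.

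No new data are needed. The real cost is that the functional form must be chosen in advance. It should be fixed before arm-level outcomes are seen, because choosing the baseline adjustment afterwards would be data-driven.

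Two further changes are optional and minor: use the continuous form in the primary model too (0-3 power points), and word 1.11 so that it names the indicators defined in 1.6.1.

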### 1.6.2 SAS Code for Primary Analysis

SAS code suitable for performing the primary analysis follows. In this code, it is assumed that non-suppression and death from any cause have been lumped together as outcomes. The p-values from the four contrasts will be used in the closed testing.

```
proc genmod data = all;  
  class arm time patid site vloadbase cd4base;  
  model outcome = vloadbase cd4base site arm time time * arm / dist = bin;
```

```
repeated subject = patid / type = exch;  
contrast "TAU NAV" arm 1 -1 0 time * arm 0 1 0 -1 0 0;  
contrast "TAU NAVCM" arm 1 0 -1 time * arm 0 1 0 0 0 -1;  
contrast "NAV NAVCM" arm 0 1 -1 time * arm 0 0 0 1 0 -1;  
contrast "TAU NAV NAVCM" arm 1 -1 0 time * arm 0 1 0 -1 0 0,  
      arm 1 0 -1 time * arm 0 1 0 0 0 -1;  
run;
```

## 1.7 Rationale for Sample Size and Statistical Power

Power calculations were based on a simulation of several scenarios, with 5000 iterations per scenario. In each iteration, 266 virally unsuppressed participants were recruited to each of three treatment groups, after which death and dropout rates, and rates of suppression before and after 6 months, were imposed so as to result in proportions of simulated participants dead, lost, suppressed, and unsuppressed at both 6 and 12 months as indicated below. These rates characterized the scenario. (Note that the rates dictate the probabilities of joint occurrences of outcomes at 6 and 12 months, but it is possible for more than one set of rates to produce the same set of 6-month and 12-month margins.)

Once these data were simulated, they were subjected to a Generalized Estimating Equation (GEE) analysis in which dropouts were ignored and dead participants were combined with unsuppressed participants. More specifically, the GEE regressed state (suppressed versus unsuppressed or dead) on time (6 months, 12 months), treatment group (Patient Navigator = PN, Contingency Management + Patient Navigator = CM, Treatment as usual = TAU) site (1-10) and the time by treatment group interaction using a binomial link. The outcome of interest was the proportion suppressed (versus unsuppressed or dead) in each arm at 12 months, but the analysis incorporated 6-month data so that the 6-month/12-month correlation could in part offset loss to follow-up between 6 and 12 months. Contrasts were used to obtain p-values for the hypotheses CM=PN=TAU, CM=PN, CM=TAU, and PN=TAU with respect to the outcome of interest.

These p-values were combined together using the closed-testing methodology explained in Section 1.6. Note was taken of which of the pairwise hypotheses were rejected ( $\alpha = 0.05$ , two-tailed), and which accepted according to the Closed testing algorithm in each iteration. Finally, the power for the tests of the various hypotheses was estimated as the proportion of the 5000 iterations in which each hypothesis was rejected.

The scenarios were defined by the following parametric values, which varied from treatment group to treatment group:

- M6 = target suppressed proportion at 6 months (assuming no death or dropout)
- M12 = target suppressed proportion at 12 months (assuming no death or dropout)
- S = Probability that a participant will be suppressed at 12 months, given he was suppressed at 6 months
- U = Probability that a participant will be unsuppressed at 12 months, given that he was unsuppressed at 6 months
- E = quarterly probability of death for a suppressed participant
- F = quarterly probability of death for an unsuppressed participant
- G = quarterly dropout probability for a suppressed participant
- H = quarterly dropout probability for an unsuppressed participant

Four scenarios (A-D) were investigated, with parametric values given by the table below:

Scenario	Group	M6	M12	S	U	E	F	G	H
A	TAU	0.18	0.16	0.95	0.99	0.02	0.05	0.04	0.04
A	PN	0.375	0.26	0.85	0.99	0.02	0.05	0.04	0.04
A	CM	0.55	0.4	0.85	0.98	0.02	0.05	0.04	0.04
B	TAU	0.175	0.16	0.98	0.99	0.015	0.03	0.03	0.03
B	PN	0.33	0.24	0.94	0.98	0.015	0.03	0.03	0.03
B	CM	0.49	0.44	0.96	0.98	0.015	0.03	0.03	0.03
C	TAU	0.175	0.16	0.98	0.99	0.02	0.05	0.04	0.04
C	PN	0.33	0.24	0.94	0.98	0.02	0.05	0.04	0.04
C	CM	0.49	0.44	0.96	0.98	0.02	0.05	0.04	0.04
D	TAU	0.18	0.16	0.95	0.99	0.015	0.03	0.03	0.03
D	PN	0.375	0.26	0.85	0.99	0.015	0.03	0.03	0.03
D	CM	0.55	0.4	0.85	0.98	0.015	0.03	0.03	0.03

The numerical values of the parameters selected in scenarios A-D were chosen to match prior experience of the investigators and data from the literature. Out of care HIV-infected individuals who are admitted to the hospital will have very low rates of viral suppression, in the range of 10-15%. From clinical discussions amongst the research team it was decided that a 10% to 12% increase (i.e., moving from 15% to 25% or 15% to 27%) is a minimally clinically meaningful change. We therefore aimed power determination at uncovering around a 12% pair-wise difference between intervention conditions. From an ongoing study of [name] and [name], a 12-15% death rate seemed to be likely in this cohort. Finally, since all participants are heavy drug and/or alcohol users it is appropriate to account for 10-15% attrition (in addition to the deaths) in these calculations even though, the research team has a history of achieving high rates of follow-up.

Power results are given in the following table, along with the parametric value of M12 and simulated resulting proportions of death, attrition, and suppression ignoring dropouts. Across each of the 4 scenarios, there is 87% power or greater to reject any of the 3 pair-wise comparisons under the assumptions set forth and a sample size of 266 study participants per treatment group.

Scenario	12-Month Statistics (percent)														
	Observed Attrition			Observed Death			Target Suppression(M12)			Realized Suppression			Power		
	TAU	PN	CM	TAU	PN	CM	TAU	PN	CM	TAU	PN	CM	TAU vs PN	PN vs CM	TAU vs CM
A	14	14	14	16	15	14	16	26	40	16	29	42	93	87	100
B	11	11	11	10	10	9	16	24	44	17	30	44	94	92	100
C	14	14	14	16	15	14	16	24	44	16	28	42	93	89	100
D	11	11	11	10	10	9	16	26	40	16	30	44	94	89	100

\* Realized Suppression Outcome = suppressed / (suppressed + unsuppressed + dead)

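### The 87% power floor is simulated for participants all unsuppressed at entry, but the planned analysis expects some to be suppressed at entry; the floor holds only under one reading of the scenario rates, and the baseline viral load flag uses a different cut from the outcome

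*SAP*

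**What the plan says.** **Power (SAP 1.7).** The simulated population is described thus: "In each iteration, 266 virally unsuppressed participants were recruited to each of three treatment groups". The rates of suppression, death and dropout are imposed after that. The fitted GEE contains time, arm, site and the time-by-arm interaction, with no baseline viral load or CD4 term. The conclusion is that "there is 87% power or greater to reject any of the 3 pair-wise comparisons under the assumptions set forth", for 266 participants per group. That closing sentence no longer says the participants are unsuppressed.

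**Primary model (SAP 1.6.1, 1.6.2, 1.11).** Besides site, the model adjusts for "an indicator of baseline CD4 count (greater than 350 cells/uL), an indicator of detectable viral load at baseline". The SAS code carries these as two class variables.

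**Secondary analysis (SAP 1.9.1, item a).** "Repeat primary analysis with the addition of a treatment interaction with viral suppression status at baseline".

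**Threshold (SAP 1.1).** Suppression is a viral load of 200 copies/ml or less. The section deliberately avoids the assay's detection limit, usually below 50, because low-level viremia is not uncommon.

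**The concern.** Three arms of 266 make 798, essentially the whole enrolment target of 800 in section 1.8, so the simulated trial has no room for anyone suppressed at entry. If the real trial had none either, everyone would be above 200 copies/ml and therefore detectable. The viral load indicator in 1.6.1 would then be constant, and the interaction in 1.9.1(a) could not be estimated. The planned analyses therefore presuppose a population that the power calculation leaves out.

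This matters because a participant already suppressed at entry has little room to improve. If such people are enrolled and the scenario rates describe only the others, every between-arm difference shrinks and the stated power belongs to a different population.

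A second, smaller matter is the baseline flag. A participant between the detection limit and 200 copies/ml already meets the success definition, yet is grouped with the viremic participants in the primary model and presumably with the suppressed participants in 1.9.1(a).

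**Working it through.** **Inputs from the SAP.** 266 per arm, and a two-sided closed test "to control family-wide type I error at 0.05 while still allowing all three pairwise comparisons between arms". The scenario A rows, in the order M6, M12, S, U, E, F, G, H, are "A TAU 0.18 0.16 0.95 0.99 0.02 0.05 0.04 0.04", "A PN 0.375 0.26 0.85 0.99 0.02 0.05 0.04 0.04" and "A CM 0.55 0.4 0.85 0.98 0.02 0.05 0.04 0.04". Scenarios B to D come from the same table.

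**Step 1: reproduce the stated power.** The trial was simulated with everyone unsuppressed at entry, suppression driven by M6, S and U, quarterly death and dropout, and death counted as failure. Each data set had a logit GEE (exchangeable, robust standard errors) with 10 sites, 12-month contrasts and the closed test; 2000 iterations per scenario.

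| Scenario | Stated TAU-PN / PN-CM / TAU-CM | Reproduced |
|---|---|---|
| A | 93 / 87 / 100 | 93.3 / 87.2 / 100 |
| B | 94 / 92 / 100 | 94.2 / 92.0 / 100 |
| C | 93 / 89 / 100 | 93.7 / 89.5 / 100 |
| D | 94 / 89 / 100 | 95.8 / 90.0 / 100 |

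All are within 2 points, and the death, attrition and realized suppression columns also match. The SAP's table is therefore right for the population it simulates.

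**Step 2: rates apply to unsuppressed entrants only.** Let f be the share suppressed at entry. Assumptions, none of them given in the SAP: f is 5%, 10% or 15%; in every arm 80% of these participants are suppressed at 6 months, and about 95% of those are still suppressed at 12 months. Treatment has no effect in them, so the arm difference is about

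difference (all) = (1 − f) × difference (unsuppressed).

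For scenario A, PN vs CM, the simulated difference at f = 0 is 41.8 − 28.5 = 13.3 points. The formula gives 13.3 × 0.95 = 12.6, 13.3 × 0.90 = 12.0 and 13.3 × 0.85 = 11.3. The simulation gives 12.6, 12.0 and 11.6.

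Power (TAU-PN / PN-CM) with the baseline flag in the GEE for f > 0, 1000 iterations per cell, simulation error about 1 point:

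| f | A | B | C | D | Lowest |
|---|---|---|---|---|---|
| 0 (step 1) | 93.3 / 87.2 | 94.2 / 92.0 | 93.7 / 89.5 | 95.8 / 90.0 | 87 |
| 5% | 90.3 / 83.7 | 91.5 / 87.9 | 90.6 / 86.2 | 93.8 / 87.9 | 84 |
| 10% | 86.9 / 81.8 | 88.9 / 86.1 | 83.7 / 82.7 | 89.2 / 84.1 | 82 |
| 15% | 81.4 / 79.4 | 83.9 / 81.3 | 79.0 / 77.6 | 86.3 / 79.6 | 78 |

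TAU vs CM stays at 99.9% or above. A second GEE run, in scenarios A and C, gave lowest values of about 86%, 84% and 79%. It started about 2 points high (89% against the stated 87% for scenario A, PN vs CM), so the lower end of each range is the better calibrated. Replacing 80% by 60% or 90% suppressed at 6 months changes scenario A, PN vs CM, little: 81.3% and 80.5% at f = 10%, and 77.2% and 76.7% at f = 15%.

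**Step 3: rates describe everyone enrolled.** M6 among the unsuppressed must then be (M6 − f × q) / (1 − f), where q is the 6-month suppression of suppressed entrants. For scenario A with f = 10% and q = 60%, PN is (0.375 − 0.06) / 0.90 = 0.350 and CM is (0.55 − 0.06) / 0.90 = 0.544. The gap among the unsuppressed widens from 0.175 to 0.194, which offsets the dilution. In scenarios A and B, at f from 5% to 15%, the lowest power with the flag in the model is 88%.

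**Step 4: what the flag contributes.** In scenario A at f = 15% and q = 90%, adding it raises TAU-PN power from 74% to 82% and PN-CM from 74% to 77%. The simulated flag is suppression status itself; the SAP's detectable flag would also put anyone between the detection limit and 200 copies/ml with the viremic.

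**Step 5: cost of a cut.** For a normal covariate with a linear effect, a cut with share p on one side keeps φ(z)² / [p(1 − p)] of the information. At the median this is 0.3989² / 0.25 = 0.64. This is only an illustration: the SAP gives no distribution for either covariate and does not say that 350 is near the CD4 median.

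**The case against.** The strongest reply is that the SAP states its 87% under its own assumptions, and under them the figure reproduces. Section 1.7 also frames the target at arm level, as a rise from about 15% to 25-27% and a pairwise difference of around 12%, which fits reading the rates as those of everyone enrolled. Under that reading nothing is lost (step 3). This stands, and it makes the loss conditional. Against it, the text places the imposed rates on participants already described as unsuppressed, so at best a key design input is ambiguous.

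A reader might go further in four ways that the document does not support.

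- **That 87% is simply overstated.** This needs a suppressed share and a smaller effect in that group. The SAP gives neither.
- **That the 10-15% suppression quoted in section 1.7 is the share suppressed at entry.** It has no time point, and the next sentence uses 15% as the starting rate for a meaningful increase. It reads as support for the TAU rate of 0.16.
- **That power falls as low as 73-78%.** Such values at 15% come from a 12-month-only logistic model with an unsourced 53% suppression rate among suppressed entrants. The planned model is a GEE using both visits.
- **That the detectable indicator is nearly uninformative.** It is constant only if nobody is suppressed at entry. Once such participants enrol it predicts outcome and recovers power (step 4).

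Adjusting for coarse prespecified indicators is also valid in a randomised trial. Continuous terms are an improvement in precision; they do not correct an error.

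**Conclusion.** The mismatch stands on the text: the power simulation excludes participants whom the primary covariate and item 1.9.1(a) presuppose, and it omits the baseline covariates of the primary model. Its effect on power is conditional. With scenario rates for unsuppressed entrants and no benefit in the rest, the floor is about 84-86%, 82-84% and 78-79% at 5%, 10% and 15% suppressed at entry, a loss of roughly 1 to 9 points from 87%. With rates for everyone enrolled, the floor holds (checked in scenarios A and B). The shares, the outcome of suppressed entrants and the lack of effect in them are all assumptions. The entry criteria are not in the SAP, so the presence of such participants is inferred from 1.6.1, 1.6.2 and 1.9.1(a).

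The two baseline cuts should be reconciled. That and the dichotomised covariates affect precision and interpretation, not the validity of the primary test.

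**What to change.** 1. In section 1.7, state whether M6 and M12 describe all enrolled or only baseline-unsuppressed participants, and state the assumed share suppressed at entry (for example 5%, 10% and 15%) with their assumed outcome by arm.
2. Re-run the GEE simulation with that mix and the planned baseline covariates, and restate the power. N does not change.
3. Use one baseline flag at 200 copies/ml or less, both in the primary model and in 1.9.1(a).
4. In 1.6.1 and 1.6.2, replace the indicators for detectable viral load and CD4 above 350 with continuous log10 viral load (undetectable values set at the assay limit) and continuous CD4, alongside the flag in item 3. The continuous terms must come off the CLASS statement. The arm contrasts are unaffected.

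The cost is SAP wording, one simulation re-run and a few changed model terms. The small downside is an assumed functional form for log viral load and CD4, which should be fixed before outcome data are seen.
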